#### 7.4.3.4 Visit 5 - Day 28 ± 3, Post-Plug Insertion

- i. Verify a subject has not used any hypotensive ocular drops since his/her last visit
- j. Record any addition, discontinuation or changes in the subject's use of any concomitant medications or ocular drops, gels or ointments since his/her last visit
- k. Record subject's temperature, heart rate and blood pressure
- l. Record subject's Best-Corrected (Glasses) Distance or Pinhole Visual Acuity
- m. Evaluate the position of each Travoprost Evolute® using the slit-lamp

- n. Perform a slit-lamp examination of each eye
- o. Record IOP measurement for each eye
- p. Record any Adverse Events/Adverse Device Event

**NOTE:** Should a study subject exit the study early (after Visit 2 and before Visit 7), the subject must undergo all test and procedures scheduled for Visit 7 (Final Visit).

#### 7.4.3.5 Visit 6 - Day 60 ± 5, Post-Plug Insertion

- q. Verify a subject has not used any hypotensive ocular drops since his/her last visit
- r. Record any addition, discontinuation or changes in the subject's use of any concomitant medications or ocular drops, gels or ointments since his/her last visit
- s. Record subject's temperature, heart rate and blood pressure
- t. Record subject's Best-Corrected (Glasses) Distance or Pinhole Visual Acuity
- u. Evaluate the position of each Travoprost Evolute® using the slit-lamp
- v. Perform a slit-lamp examination of each eye
- w. Record IOP measurement for each eye
- x. Record any Adverse Events/Adverse Device Event

**NOTE:** Should a study subject exit the study early (after Visit 2 and before Visit 7), the subject must undergo all test and procedures scheduled for Visit 7 (Final Visit).

#### 7.4.3.6 Visit 7 - Day 90 ± 7, Post-Plug Insertion (Final Study Visit)

At this visit the following will be performed and recorded:

- a. Verify a subject has not used any hypotensive ocular drops since his/her last visit
- b. Record any addition, discontinuation or changes in the subject's use of any concomitant medications or ocular drops, gels or ointments since his/her last visit
- c. If performed at SCREENING Visit, perform a urine pregnancy test on a female subject of child-bearing potential
- d. Record subject's temperature, heart rate and blood pressure
- e. Record subject's Best-Corrected (Glasses) Distance or Pinhole Visual Acuity
- f. Evaluate the position of each Travoprost Evolute using the slit-lamp prior to removal of the plug
- g. Perform a slit-lamp examination of each eye prior to study plug removal
- h. Record IOP measurement for each eye before study plug removal

- i. Removal of the study plug from each eye (refer to [Section 6.1.7](#) for details regarding removal of a punctal plug)
- j. Record any reported Adverse Events/Adverse Device Event

An exit form will be completed at the final study examination (Visit 7), or whenever the study subject completes or leaves the study for any reason.

**NOTE:** The day each Travoprost Evolute® are removed with no addition follow-up required, will be the study subject's official exit date from the study. However, **if the subject is exiting from the study due to an AE/SAE or ADE/SADE, the study subject will be followed and exam findings recorded by the investigator until the AE/SAE or ADE/SADE has resolved or has become medically stable.**

Schedule of Assessments, Events							
Visit Examination Parameters	Visit 1 Screening	Visit 2 (Day 0)	Visit 3 (Day 1)	Visit 4 (Day 7)	Visit 5 (Day 28)	Visit 6 (Day 60)	Visit 7 (Day 90)
Informed Consent/HIPAA	1						
Medical Hx (past 6 months)/Demographic Data	1	2 A					
Urine Pregnancy Test (Only women of childbearing potential)	1 B						7 B
Concomitant Med Use	1	2	3	4	5	6	7
BT (temperature), BP (blood pressure), HR (heart rate)	1	2	3	4	5	6	7
Evaluate study plug position prior to any eye exam		2*	3	4	5	6	7
Best-Corrected Distance (Glasses) or Pinhole VA	1	2	3	4	5	6	7
Automated Perimetry (Not required if measured in last 6 months)	0						
Pachymetry (Not required if documented in patient's chart)	0						
Slit-Lamp Examination	1	2	3	4	5	6	7
IOP (Goldmann) Evaluation (To be measured between 8 and 10 am)	1	2	3	4	5	6	7
Non-Dilated Fundus Examination (Include evaluation of the LENS)	1						
Begin Six-Week Washout (D/C all topical drops, gels, ointments)	1						
Punctal Size Evaluation, Dilation of Lower Puncta		2					
Insertion of Punctal Plugs		2					
**Punctal Plug Extrusion			☆ C	☆ C,D	☆ C,D	☆ C,D	7
Removal of Punctal Plugs after eye exam completed†							7‡
Adverse Event/Adverse Device Event Recording		2	3	4	5	6	7

**Keys to Abbreviations:**

- A = Verify no change in medical history, subject still meets all study inclusion/exclusion criteria
- B = If performed at the screening visit, must be performed when subject exit the study
- C = In a subject where both eyes qualified at Visit 2, if a plug is extruded in one eye, **plug is to be replaced** and subject continues in the study
- D = In a subject where only one eye qualified at Visit 2, if the plug is extruded in the qualified eye, the subject will be DISCONTINUED and replaced. In a subject where both eyes qualified, if a plug is extruded in one eye, then extruded again or in the fellow eye, the subject will be DISCONTINUED and replaced
- \* = Plug position evaluated after eye exam and plug insertion
- † = If subject EXITs the study after visit 2, but before visit 7, subject must return to Investigator's office to have plugs removed

Body Temperature:	Temperature maybe taken using a non-contact (Infrared) thermometer or orally. Oral temperatures should not be taken within five minutes of ingestion of any food or drink
Heart Rate:	Heart rate taken in the sitting position after subject has rested for 5 minutes. Recorded values can be obtained electronically (automated) or manually (observed for 30 seconds or more)
Blood Pressure:	Blood pressure, taken in the sitting position after subject has rested for 5 minutes. Recorded values can be obtained electronically (automated) or manually
Plug Position Evaluation:	Position of the plug will be evaluated as either: Normal, Present but requires adjustment, Extruded/Recovered, Extruded/Lost, Other
Slit-Lamp Exam:	Evaluation will include the Lids (Upper & Lower), Conjunctiva (Bulbar & Palpebral) and the Cornea. SL Findings will be graded on a 5-point scale: 0 = None, 1 = Trace, 2 = Mild, 3 = Moderate, 4 = Severe
IOP Evaluation:	Goldmann applanation tonometry will be used for measuring IOP. Just prior to the start of the study, the tonometer should be calibrated. IOP of each eye will be measured twice, alternating between the eyes. The average of the two measurements will be used for analysis. However, if there is a $\geq 3$ mmHg difference between the 1 st and 2 nd measurement for an eye, a 3 rd measurement will be taken and the average of the two closest values of the three will be used for analysis for that eye.

## 7.5 Unscheduled Visit

The investigator has the option of bringing a study subject back in for an unscheduled visit any time during the washout or treatment phase of the study for safety reasons (e.g., subject complaint of moderate or severe ocular symptoms, an AE). An unscheduled visit CRF should be completed. At minimum the investigator should record the following:

- a. Record any change in concomitant medication use
- b. Inspection of both punctal plugs via the slit-lamp
- c. Slit-Lamp examination, both eyes
- d. Measure IOP, both eyes
- e. Recording of any reported adverse events/adverse device events

## 7.6 Early Exit Visit (Disqualified, Discontinued or Terminated Study Subject)

Any study subject exiting the study early must undergo all test and procedures scheduled for Visit 7 (Day 90 ± 7 days, post-plug insertion) and all results recorded on the appropriate CRFs.

**NOTE:** Refer to [Section 7.4.3.6](#) for details on procedures and examination to take place on the final study subject visit

An exit CRF (Case Report Form) will be completed whenever the study subject completes or leaves the study for any reason. A study subject will be exited from the study on the day the Travoprost Evolute® are removed from both eyes with no additional follow-up required. However, **if the subject is exiting from the study due to an AE/ADE, the study subject will be followed and exam findings recorded by the investigator until the AE/ADE has resolved or has become medically stable.**

## 7.7 Emergency Anaphylactic or Overdose Procedures, Dose Modifications

Dose modification of the study drug/device is not possible or required in this study.

**NOTE:** Use caution when inserting a study plug to a subject who has previously exhibited sensitivities to phenylacetic acid derivatives and salicylate hypersensitivity as the potential for cross-sensitivity exists. This study is not expected to cause AEs different in type or intensity from those previously reported in published clinical research literature regarding the use of topical travoprost ophthalmic solutions 0.004% & 0.003% (TRAVATAN®, TRAVATAN Z®, IZBA®). Refer to the Investigator Brochure and Appendices [I](#), [J](#) & [K](#) for additional information.

Should a subject experience a significant medical issue, the subject may be treated according to the Investigator's medical judgment. Any changes, discontinuation or addition of a topical or systemic medication(s) must be recorded on the Concomitant Medication CRF.

## 7.8 Concomitant Medication

During the washout and treatment phases of the study, each subject will be instructed not to use any other ocular drops, gels or ointments in his or her eyes that have not been prescribed by the investigator. Systemic or topical medications that are being used at the Screening Visit, that are considered necessary for the subject's welfare and are permitted by the protocol ([Section 5.2.1.2](#) for details), may continue to be used as long as the concentration and dosing frequency of the medication(s) remains the same throughout the entire washout and treatment phases of the study.

### 7.8.1 Pre-Study Concomitant Medication Use

Pre-study concomitant medication is defined as a prescription and/or an over-the-counter (OTC) medication taken within 2 months (whether continuing or not) prior to Visit 1 (Screening Visit). All prior medications must be documented on the Concomitant Medications CRF.

### 7.8.2 Concomitant Medication Use during Study

Each study subject will be instructed not to use any other ocular drops, gels or ointments in his/her eyes that have not been prescribed by the Investigator. Systemic medications being used at screening visit that are permitted by the study protocol (see inclusion/exclusion criteria for details), are considered necessary for the study subject's welfare, and will not interfere with the study may be used.

All prescription systemic, ophthalmic and over-the-counter concomitant medications used during the washout and treatment phase of the study, that are considered necessary for the study subject's welfare, and will not interfere with the study, may be used but must be documented on the Concomitant Medication CRF. The use of all concomitant medications during the study, except for routine medications given for ocular study procedures required by the protocol (i.e., topical anesthetic for plug insertion), will be documented. The medication name, start and stop dates, indication, dose, route of administration and any dosing alterations must be documented on the Concomitant Medications CRF through completion of the last study visit.

Systemic or topical medications that are being used at the Screening Visit, that are considered necessary for the subject's welfare and are permitted by the protocol ([Section 5.2.1.2](#), criteria 12 & 18, for details), may continue to be used as long as the concentration and dosing frequency of the medication(s) will remain the same throughout the entire duration of the study.

## 7.9 Prohibited Medications, Treatments and Procedures

### 7.9.1 Prohibited Medications

After the screening visit, the use of any ocular drops, gels or ointments in either eye is prohibited, with the exception for routine topical medication given for an ocular study procedure(s) that is required by the protocol (i.e., topical anesthetic). Systemic or topical medications being used at

the Baseline Visit that are permitted by the protocol ([Section 5.2.1.2](#), criteria 12 & 18, for details), are considered necessary for the subject's welfare, and will not interfere with the study may be used.

### 7.9.2 Prohibited Treatments

The following are prohibited during the study washout and treatment periods:

- a. Use of homeopathic remedies (e.g., gingko biloba, cayenne pepper, bilberry, etc.)
- b. Significant changes to eating or drinking habits (i.e., begin a diet, increase or decrease alcohol, caffeine or water intake, etc.)
- c. Significant changes in physical exercise/yoga
- d. Use of marijuana

### 7.9.3 Prohibited Procedures

The following procedures are prohibited during the study washout and treatment periods:

- a. Laser trabeculoplasty
- b. Trabeculectomy
- c. Tube shunt surgery
- d. Cataract surgery

## 7.10 Rescue Medication(s)

### 7.10.1 Administration of a Rescue Medications

A subject with an elevated IOP (>34 mmHg) or undue medical risk in either eye should be prescribed his/her glaucoma regimen they were using prior to entering the study. The use of a rescue medication will be considered prohibited medication and will be considered a protocol deviation and the study subject will be terminated from the study. Reason for termination on the exit form should be listed as "due to lack of efficacy".

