## iii. Treatment Phase

- a. **INCLUSION Criteria:** After the washout phase, the following are requirements a subject must meet in order to be considered for enrollment into the treatment phase of the study:
  1. After the six-week washout phase, the subject continues to meet all screening and washout inclusion/exclusion study criteria
  2. After the six-week washout phase, subject's Baseline (Visit 2) IOP measured between 8:00 and 10:00 AM, is between  $\geq 23$  and  $\leq 34$  mmHg in at least one eye
  3. Subject's Baseline (Visit 2, morning average) IOP is  $\geq 5$  mmHg from the subject's SCREENING (pre-washout) IOP in at least one eye whose Baseline IOP is between  $\geq 23$  and  $\leq 34$  mmHg
  4. Investigator is able to dilate the lower puncta of each eye to 1.0 mm, and insert a study plug into each puncta.
- b. **EXCLUSION Criteria:** If any of the below criteria apply to a study subject that has completed the washout period, the subject does not qualify for enrollment into the treatment phase of the study:
  1. A subject who no longer meets all the screening and washout study criteria
  2. A subject who cannot be successfully inserted with a Travoprost Evolute® in the lower puncta of each eye, even if only one eye qualifies for enrollment.

**STUDY VARIABLES:** The following will be performed and/or recorded during the course of the study:

- a. Obtain written HIPAA and Informed Consent
- b. Verify a subject has not used any hypotensive ocular drops within the last 12 hours prior to the screening visit or at any time during the washout or treatment phases of the study
- c. Record any changes in the subject's use of any concomitant medications or ocular drops, gels or ointments during the course of the study
- d. Record subject's demographic data and medical history for past 6 months

- e. Perform a urine pregnancy test on a female subject of child-bearing potential at their screening and last study visits
- f. Measure subject's temperature, heart rate and blood pressure
- g. Record subject's Best-Corrected (Glasses) Distance or Pinhole Visual Acuity
- h. Verify documented automated perimetry results have been measured in the last 6 months  
**NOTE:** If perimetry measurement are older than 6 months, perform automated perimetry at the screening visit.
- i. Verify corneal thickness measurements are documented in the subject's chart  

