### 5.2.1.2 Screening Phase - EXCLUSION Criteria

If any of the below criteria apply to a potential study subject, the subject does not qualify for enrollment into the screening phase of the study:

1. A subject with a history of non-response to topical prostaglandin eye drops for OAG/OH
2. A subject with angle-closure glaucoma, neovascular glaucoma, traumatic glaucoma or iridocorneal endothelium syndrome in either eye
3. A subject with a known sensitivity to travoprost, fluorescein, topical anesthetic, silicone, any inactive ingredient of the Travoprost Evolute® or any other products required for study procedures
4. A subject with  $\geq 0.9$  vertical cup or completely notched optic nerve head rim in either eye
5. A subject with any functionally significant visual field loss or progressive field loss within the last year in either eye
6. A subject with a history of complications, AEs, trauma or disease in the nasolacrimal area, whether or not it was due to punctal plug wear, including but not limited to dacryocystitis, inflammation or canaliculitis in either eye
7. A subject with a history of intolerance to punctal plugs or a known sensitivity to any inactive ingredient of the punctal plug, silicone, topical anesthetic, or any other products required for the study
8. A subject with structural lid abnormalities (i.e., ectropion, entropion) in either eye
9. A subject with an active lid disease in either eye (i.e., moderate or severe blepharitis, meibomianitis) that requires medical treatment
10. A subject with any clinically significant (moderate or severe) lid, conjunctival or corneal findings in either study eye at the screening visit
11. A subject with a history of chronic/recurrent inflammatory eye disease (i.e., scleritis, uveitis, herpes keratitis) in either eye
12. A subject who would require the use of any ocular medication(s), an over-the-counter drop(s), ointment(s) or gel(s), other than the study hypotensive medication(s) in either eye during the study period
13. A subject who has had any ophthalmic surgical procedures (i.e., glaucoma laser, minimally invasive glaucoma surgery, cataract, refractive, etc.) in either eye within the last six months or will require ophthalmic surgery before completing the study
14. A subject with a history of penetrating keratoplasty in either eye
15. A subject requiring the use of a contact lens in either eye at any time during the study period

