### 5.2.3 Study Treatment Phase Criteria

#### 5.2.3.1 Treatment Phase - INCLUSION Criteria:

After the washout phase, the following are requirements a subject must meet in order to be considered for enrollment into the treatment phase of the study:

- 1) After the six-week washout phase, the subject continues to meet all screening phase inclusion/exclusion criteria
- 2) After the six-week washout phase, subject's Baseline (Visit 2) IOP, measured between 8:00 and 10:00 AM, is  $\geq 23.0$  and  $\leq 34.0$  mmHg in at least one eye

- 3) Subject's Baseline (Visit 2, morning average) IOP is  $\geq$  5 mmHg from the subject's SCREENING (pre-washout) IOP in at least one eye whose Baseline IOP is between  $\geq$  23 and  $\leq$  34 mmHg.
- 4) Investigator is able to dilate the lower puncta of each eye to 1.0 mm, and insert a study plug into each puncta.

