#### 5.2.3.2 Treatment Phase - EXCLUSION Criteria

If any of the below criteria apply to a study subject that has completed the washout period, the subject does not qualify for enrollment into the treatment phase of the study:

- 1) A subject who no longer meets all the screening and washout study criteria
- 2) A subject who cannot be successfully inserted with a Travoprost Evolute® in the lower puncta of each eye, even if only one eye qualifies for enrollment.

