#### 5.4.3 Handling of Study Subject Termination, Discontinued or Disqualified

##### 5.4.3.1 Handling of Terminated Study Subject

A terminated study subject will return to the clinic for an end of study safety evaluation and the removal of his/her punctal plugs. A terminated study subject will receive appropriate treatment at the discretion of the Investigator. Notification of termination will be clearly documented on the appropriate Case Report Form. A terminated study subject is considered to have completed the study and **will NOT be replaced**.

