#### 7.4.3.1 Visit 2 - Day 0, Plug Insertion Visit (Baseline)

Qualified subject will undergo the following:

- a. Verify a subject has not used any hypotensive ocular drops during the washout phase
- b. Verify whether there are any changes in the medical history and confirm the subject still meets all study inclusion/exclusion criteria
- c. Record any addition, discontinuation or changes in the subject's use of any concomitant medications or ocular drops, gels or ointments during study washout phase
- d. Record subject's temperature, heart rate and blood pressure
- e. Record subject's Best-Corrected (Glasses) Distance or Pinhole Visual Acuity
- f. Perform a slit-lamp examination of each eye
- g. Record IOP measurement for each eye
- h. Record any Adverse Events/Adverse Device Event.

After the baseline procedures and examinations have been completed, a subject that meets the baseline IOP inclusion criteria ([Section 5.2.3](#)) will have their punctal size of each eye evaluated and will be inserted with a Travoprost Evolute into the lower puncta of each eye even if only one eye qualifies.

- i. Dilate the lower puncta to 1.0 mm and insert a study plug into the lower punctum of each eye (refer to Sections [6.1.5.2](#) & [6.1.5.3](#) for details regarding punctum dilation and punctal plug insertion techniques)
- j. Evaluate after insertion, the position of the study plugs in each eye using the slit-lamp

**NOTE:** At the conclusion of the visit a subject does not meet all treatment inclusion/exclusion criteria or the investigator is unable to insert a Travoprost Evolute into the lower puncta of each eye, the study subject will be discontinued from the study. The subject ID number will be retired. If the investigator was able to insert only one study plug, the one inserted study plug must be removed ([Section 5.4](#))

Each study subject will be instructed not to attempt to remove or adjust the punctal plug on his/her own. In addition, encourage each study subject to restrict eye rubbing, swimming, scuba diving, or other actions or activities that may result in physical manipulation of the eye region

Each study subject will be scheduled to return the next day for a follow-up study examination (Visit 3, day 1 post-plug insertion).

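### The 34 mmHg entry ceiling binds only one eye, so a subject whose fellow eye is already above the rescue level at Visit 2 meets the IOP criteria for plugs in both eyes

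*Combined protocol and SAP*

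**What the plan says.** Treatment inclusion 2 (5.2.3.1, repeated in the synopsis) asks for a Visit 2 IOP of 23.0 to 34.0 mmHg "mmHg in at least one eye". Inclusion 3 asks for a difference of at least 5 mmHg from the screening "IOP in at least one eye whose Baseline IOP is between" 23 and 34 mmHg, so it too concerns only an eye already inside the window.

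The two treatment-phase exclusions (5.2.3.2) are loss of the screening or washout criteria and failure to insert a plug in each eye, the latter applying "even if only one eye qualifies for enrollment". Section 7.4.3.1 then inserts a plug into the "lower puncta of each eye even if only one eye qualifies".

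The rescue rule in 7.10.1 is an either-eye rule. It covers "A subject with an elevated IOP (>34 mmHg) or undue medical risk in either eye" and says the pre-study regimen should be prescribed again. Use of rescue leads to termination: "Reason for termination on the exit form should be listed as" due to lack of efficacy. Under 5.4.3.1, "A terminated study subject is considered to have completed the study" and is not replaced.

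Post-washout pressures above 34 mmHg are tabulated by patient and by eye (10.4.3). The section attaches no eligibility consequence to them.

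**The concern.** The entry ceiling and the rescue threshold use the same number but count eyes differently. Entry needs one eye at or below 34 mmHg; rescue is triggered by either eye above it. One set of Visit 2 readings can therefore satisfy both.

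Two things follow. The first concerns participant safety: an eye at a level where the plan says treatment should be restarted can instead be sent home on a delivery system whose effect is what the study sets out to learn. The second concerns the meaning of the exit code. If that eye is still above 34 mmHg at the next visit, the subject is rescued and recorded as a lack-of-efficacy exit, and is not replaced, although the pressure was above the threshold before any plug was placed.

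**Working it through.** **Eligibility logic.** The plan gives no figure to reproduce here, so I applied the criteria to a test subject: screening 18/19 mmHg, Visit 2 28/36 mmHg.

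- Inclusion 2: met, because 28 lies in 23 to 34 in one eye.
- Inclusion 3: met, because 28 − 18 = 10, which is at least 5, in the qualifying eye.
- Inclusion 4 and exclusion 2: met if both puncta dilate and accept plugs.
- Exclusion 1: sends the site back to the screening and washout criteria. The limit of less than 22 mmHg in both eyes belongs to the pre-washout visit. It cannot be a Visit 2 cap, since no subject at 23 mmHg or more could then enter.
- Rescue level (7.10.1): already exceeded, because 36 > 34 in one eye.

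The next scheduled IOP is Visit 3, Day 1 (7.4.3.2).

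**How often.** The documents give no between-eye data, so frequency rests on a model.

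SDs come from the baseline rows of Appendix K, Table 1, using SD = SE × √N:

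- 8 AM: 0.12 × √442 = 2.52; 0.14 × √418 = 2.86
- 10 AM: 0.13 × √442 = 2.73; 0.15 × √418 = 3.07

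The matching means are 26.9 and 27.1 at 8 AM, and about 25.5 at 10 AM (25.4 and 25.6). For screening IOP on treatment I used a mean of about 19.3 and an SD of 3.4 (0.16 × √442 = 3.36).

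Assumed: normality, between-eye correlation 0.5 to 0.8, and baseline-to-on-treatment correlation 0.5. I took 2 million simulated subjects per case, with readings on a 0.5 mmHg grid. The event is a subject who meets the criteria with the other eye above 34 mmHg.

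| Post-washout mean, SD | Window only | All IOP criteria | Per 30, all IOP criteria |
|---|---|---|---|
| 25.5, 2.73 | 0.11–0.14% | 0.02% | 0.01 |
| 25.5, 3.07 | 0.34–0.44% | 0.08–0.10% | 0.02–0.03 |
| 26.9, 2.52 | 0.26–0.34% | 0.06–0.07% | 0.02 |
| 27.1, 2.86 | 0.85–1.13% | 0.25–0.31% | 0.08–0.09 |
| 26, 3.5 (assumed) | 1.30–1.74% | 0.46–0.58% | 0.14–0.17 |
| 27, 4 (assumed) | 4.2–5.8% | 2.1–2.7% | 0.63–0.81 |

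Per 30 is 30p; for example, 30 × 0.0031 = 0.09. The chance of at least one such subject is 1 − (1 − p)^30: about 9% at p = 0.31%, and about 56% at p = 2.7%.

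The all-criteria column is the relevant one, because every enrolled subject must also screen below 22 mmHg in both eyes and show the 5 mmHg rise. It is sensitive to the assumed baseline-to-on-treatment correlation. At 0.3 the highest Appendix K case becomes 0.51–0.66% (0.15–0.20 per 30) and the SD 4 case 3.1–4.1% (0.93–1.24 per 30). At 0.7 they fall to 0.05–0.06% and 0.90–1.11%.

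At Appendix K SDs the high eye averages 34.8 to 35.2 mmHg, so the 36 mmHg in the test subject is towards the upper end.

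**The case against.** The best reply is that the plan already stops this subject. Section 7.10.1 names no visit. Applied at Visit 2, it would put the subject back on drops. The subject would then need ocular medication during the study (screening exclusion 12) and could not stay off hypotensives (5.2.2). Both are re-checked before insertion, and the note in 7.4.3.1 discontinues anyone who fails. Exclusion 19 and the undue-risk wording offer discretionary stops as well. This has force: it would be too strong to call the subject eligible outright, and the point is limited to meeting the IOP criteria. But the chain is an inference. Exclusion 12 does not mention pressure, and the efficacy wording of 7.10.1, with plug removal for terminated subjects in 5.4.3.1, suggests a rule for treated subjects. Two careful sites could act differently.

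It is also fair that the high eye receives active drug, that it is typically only about 1 mmHg over the limit, and that it is measured again next day, with unscheduled visits allowed (7.5). That keeps the safety gap small. One-eye qualification with bilateral insertion is plainly deliberate, and nothing here argues against it.

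A reader might go further and infer that a subject caught at Visit 2 would be coded as lack of efficacy and use up one of the 30 places. The documents do not support that. The synopsis and 5.1 describe the 30 as subjects with plugs inserted, 10.1 requires insertion for the primary population, and 7.4.3.1 treats Visit 2 failures as discontinued, which 5.4.3.2 says are replaced.

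**Conclusion.** The point holds at minor severity. On the text, a subject at 28/36 mmHg meets all the IOP entry criteria while above the plan's either-eye rescue level, and no criterion explicitly closes the gap. What is at stake is about one day's exposure of an eye above the rescue level and, if that eye stays above 34 mmHg, a lack-of-efficacy exit that reflects a pre-treatment pressure.

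The expected number is about 0.01 to 0.10 per 30 at Appendix K SDs, and up to about 0.8 at an assumed SD of 4, both with an assumed baseline-to-on-treatment correlation of 0.5. A correlation of 0.3 would raise the upper ends to about 0.2 and 1.2. The eligibility logic needs none of these assumptions; only the frequency does.

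A reader might also infer bias in the primary mean, since 10.4.2 analyses the eye with the highest post-washout IOP. That is not claimed: 10.4.2 does not settle whether a non-qualifying eye can be the study eye, and the event is rare.

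**What to change.** In 5.2.3.1(2) and the synopsis, require a Visit 2 IOP of 23.0 to 34.0 mmHg in at least one eye and no more than 34.0 mmHg in both eyes. A subject who fails this is not inserted, resumes prior therapy, is recorded as a Visit 2 failure under 7.4.3.1, and is counted in the existing 10.4.3 line for IOP above 34 mmHg after washout.

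Optionally, state in 7.10.1 that the lack-of-efficacy code applies only to readings taken after plug insertion.

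The cost is one clause in two places, plus one more if the option is taken. Expect at most about one extra baseline failure per 30 enrolled, and far fewer at Appendix K SDs. No visit, measurement or table is added.
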